#### **Methods and Procedures**

##### Visit 1 -- Recruitment and Enrollment:

The study will employ convenience sampling of surgical candidates with glenohumeral osteoarthritis from the practice of the primary investigator, who is the treating surgeon. Immediately following his or her clinical visit with the primary investigator, each patient who is a candidate for shoulder arthroplasty will receive information on the study, including benefits and harms of participating in the study from the co-investigator at primary investigator's clinical office (NYU Langone Orthopedic Center). Written consent will be obtained from subjects based upon their medical condition (as determined by their physician). The consent process will take place during an office visit at which time the investigator has determined subject's voluntary participation has been upheld. Subjects will be informed about the study and the intended purpose. They will be given the opportunity to ask questions and receive thorough explanations. They will be made aware of the possible risks and anticipated benefits. They will also be informed of alternative procedures. Subjects will then be given another opportunity to ask questions and agree or disagree to consent. Potential subjects may enroll by providing informed consent with the co-investigator. The study will not exclude potential participants based on sex, race, and/or ethnicity. Subsequently, the study co-investigator will determine subject eligibility to participate in the study by obtaining information on potential contraindications of MR imaging, such as having prior history of injury involving metal or metallic particles as well as presence of medical implants, such as cardiac pacemakers.

This recruitment and enrollment visit should take no more than thirty (30) minutes.

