### **Study Design**

Prospective, unrandomized, double blinded, self-controlled clinical trial

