## II. CHARACTERISTICS OF THE RESEARCH POPULATION

### **Number of Subjects**

A total of fifty (50) patients will be enrolled in this study.

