### **Inclusion Criteria**

- Males and females ages 18 or more;
- Patients suffering from glenohumeral OA;
- Radiographic evidence of severe glenoid erosion;
- Indication for TSA based on clinical exam;
- Patient is willing and able to review and sign a study informed consent form.

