### III. METHODS AND PROCEDURES

#### **Sample Size Analysis**

Using SAS software, version 9.4 (SAS Institute Inc., Cary, NC, USA) based on paired t-test analysis, for alpha = .05 and power = .80, ten pairs are required, at minimum, for the study.

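### Convenience sampling from the surgeon-investigator's practice conflicts with the promise to inform every candidate and allows untraceable selection; consecutive invitation with a log would reduce it

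*Combined protocol and SAP*

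**What the plan says.** The section on Visit 1 (Recruitment and Enrollment) names the sampling method and the source: "The study will employ convenience sampling of surgical candidates with glenohumeral osteoarthritis from the practice of the primary investigator, who is the treating surgeon". The sentence after it says that, straight after the clinic visit, "each patient who is a candidate for shoulder arthroplasty will receive information on the study", and that the co-investigator gives this information. Entry then depends on consent: "Potential subjects may enroll by providing informed consent with the co-investigator". The co-investigator checks MR contraindications after that.

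Among the Inclusion Criteria is "Radiographic evidence of severe glenoid erosion", with no threshold or grade. The target under Number of Subjects is fixed: "A total of fifty (50) patients will be enrolled in this study". Under Visit 2, every subject has both CT and MR, scheduled for the same day at two facilities.

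No section says that enrolment is consecutive or random. The list under Types of Data in the monitoring plan covers images, interpretations, reportable or adverse events, and deviations. It has no count of candidates seen, invited, declining or not scanned.

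**The concern.** The two adjacent sentences can lead to different samples. Convenience sampling, in its usual sense, lets the team enrol whichever eligible patients are easiest to enrol. Informing every candidate is close to consecutive recruitment. A team could follow either and comply with the protocol, and because no screening counts are kept, a reader of the results could not tell whether the 50 are the first 50 eligible and willing patients or some other subset.

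This matters because of what the study estimates. Outcome Measure Evaluation Criteria gives the outcome as the degree of concordance or discordance between 3D CT and 3D MR, and the objective is noninferiority. Agreement between two measurements depends on the patients measured. If patients whose MR models are harder to build or read are under-represented, the observed spread of CT-MR differences may not describe the population in which MR would replace CT. Pairing cannot repair this, because entry is decided before either scan.

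**Working it through.** **The plan's only computed figure.** Sample Size Analysis states: "based on paired t-test analysis, for alpha = .05 and power = .80, ten pairs are required, at minimum, for the study". It gives no effect size or SD of differences, so the ten pairs can be neither confirmed nor refuted. Solving the paired t-test power function (noncentral t, 9 df) backwards, ten pairs with 80% power at alpha 0.05 correspond to a standardized difference of about 1.00 two-sided or 0.85 one-sided. The present point does not depend on this: a change in the entry rule alters neither the ten pairs nor the 50 subjects.

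**The passages side by side.**

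| Step | What the protocol provides | Room for discretion |
|---|---|---|
| Source | One surgeon-investigator's practice | Fixed to one practice |
| Sampling label | Convenience | Yes, by the label |
| Approach | Every arthroplasty candidate informed by the co-investigator | None, if followed |
| Eligibility | Severe erosion without a threshold; ability to comply | Judgement |
| Consent and MR check | By the co-investigator | Refusal and exclusion, not counted |
| Record of the above | None listed | Not traceable |

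**What pairing protects.** Each subject supplies a CT and an MR value, so patient characteristics are the same on both sides. Selection therefore does not confound CT versus MR. What it can change is the distribution of the within-patient differences.

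**Illustration 1: spread.** All inputs are assumed. A share p of eligible patients is hard to scan, with an SD of CT-MR differences of 5 degrees; the rest have 2.5 degrees; mean differences are equal. In the full series, SD = sqrt((1 - p) x 2.5^2 + p x 5^2).

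- p = 0.20: sqrt(0.8 x 6.25 + 0.2 x 25) = sqrt(10) = 3.16. A sample without them has 2.5, and 1 - 2.5/3.16 = 21% narrower.
- p = 0.10: sqrt(0.9 x 6.25 + 0.1 x 25) = sqrt(8.125) = 2.85, and 1 - 2.5/2.85 = 12% narrower.

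At p = 0.20, the half-width of 95% limits of agreement would be 1.96 x 2.5 = 4.9 degrees instead of 1.96 x 3.16 = 6.2 degrees.

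**Illustration 2: mean.** If a share f of eligible candidates enters and the mean CT-MR difference in those missed differs by g SD, the sample mean is off by (1 - f) x g. For f = 0.9 and g = 0.25 this is 0.1 x 0.25 = 0.025 SD; for f = 0.5 and g = 1.0 it is 0.5 x 1.0 = 0.50 SD. The documents give neither f nor g.

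**Direction.** With equal means, a smaller SD works differently in different analyses. It narrows limits of agreement or a noninferiority interval, which helps MR. Data Analysis, however, specifies a paired t-test of difference. For the same mean difference and n, t grows by 3.16/2.5 = 1.26 at p = 0.20 and by 2.85/2.5 = 1.14 at p = 0.10, so a CT-MR difference is easier to detect, which works against MR. No single direction follows from the plan.

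**The case against.** The strongest defence is that this may be loose wording. Convenience can be read as describing the accessible source, one practice, with the next sentence saying how patients in it are approached. On that reading the two sentences do not conflict. The co-investigator, not the surgeon, informs patients, takes consent and checks contraindications. The design is paired, the sampling method is openly disclosed, and the Exclusion Criteria already leave out patients without the physical or mental ability to comply, so some hard-to-scan patients would be absent under any entry rule.

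Much of this stands. A reader might infer that the surgeon hand-picks patients who are easy to scan, or that the sample is tilted in favour of MR. The documents support neither. They describe no rule by which anyone chooses among candidates, they do not mention choosing by body habitus or scanner availability, and requiring severe erosion does not obviously favour easy anatomy. The illustration also makes the extreme assumption that convenience entry misses every hard case and consecutive entry captures all of them.

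The defence does not remove the ambiguity. The stated method is still convenience sampling, nothing elsewhere overrides it, and no record would show that every candidate was in fact approached.

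**Conclusion.** The point holds as a matter of case mix and generalizability, not of confounding. The stated sampling method permits discretionary choice among eligible patients, the adjacent sentence describes something stricter, and nothing planned would reveal which was done. The possible effect is on the CT-MR agreement estimate. Its size and direction are unknown from the documents; the narrowing of the SD by 12% to 21% rests wholly on the assumed 10% to 20% share, the two assumed SDs and equal means, and is not an estimate for this trial.

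A reader might also infer that consecutive entry would eliminate selection. It would not. It ends discretionary choice among eligible candidates, but refusals, MR exclusions, the single practice and the undefined severity criterion would remain. The change is worth making because it replaces a stated weaker method with a better one for little effort; it is not a flaw that invalidates the study.

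**What to change.** In the Visit 1 section, replace convenience sampling with consecutive invitation: from study start, every candidate in the practice who meets the Inclusion and Exclusion Criteria is invited in order of presentation until 50 are enrolled. This also reconciles the two sentences.

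Have the research coordinator, who already documents study data in a spreadsheet, keep counts of candidates seen, eligible, invited, declining and not scanned, with reasons. Report these counts with the results, and state the single-surgeon source as a limit on generalizability.

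The cost is an edit to one sentence, a short log, and some loss of freedom in scheduling CT and MR on the same day. That this is small is an inference, since every candidate is already to be informed; the documents give no patient-flow figures. Aggregate counts should suffice. Any further data on patients who decline, such as age or erosion, may need IRB agreement, because the consent and data-storage sections provide only for participants. The planned 50 subjects and the ten-pair minimum are unchanged.

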##### Visit 2 -- Preoperative Imaging:

Subjects will have both 3D CT and 3D non-contrast MR scheduled on the same day. The CT scan, which is standard of care, will be scheduled at NYU Langone Orthopedic Hospital followed by the MR, the investigational procedure, at NYU Langone Orthopedic Center. Before imaging, the subjects will be screened for potential contraindications to each imaging modality in accordance with institutional standard of care routine procedures. The standard of care CT imaging will take no more than 30 minutes while the investigational MR imaging will take no more than 60 minutes in duration. Each enrolled subject will receive a standard of care CT scan along with an investigational MRI scan of the shoulder girdle while supine. Each enrolled subject's CT imaging is not dependent on receiving prior MR imaging; he/she will not experience delays in receiving standard of care CT imaging as a result of study participation.

The CT protocol consists of 3-mm axial images of the glenoid reconstructed into 1-mm sagittal and coronal 2D reconstructions using the following parameters: 120 kV, 280 mA, and pitch of 0.9. The CT data were also used to produce a 3D reconstruction of each glenoid.

The 2D glenoid version is measured by 2 musculoskeletal-trained radiologists on 2 occasions, at a minimum of 2 weeks apart, with the observers blinded to each other's results. The 2 observers meet before obtaining data to review the appropriate technique for measuring glenoid version. The 2D glenoid version is determined using the method of Friedman et al (17) with the mid glenoid cut being determined by dividing the total number of axial cuts through the glenoid by 2 (20).

The 2D CT images are imported in Vitrea software. The 3D volume rendering model will be produced. The 3D glenoid version is measured by the same 2 observers on 2 occasions, at a minimum of 2 weeks apart, with the observers blinded to each other's results. Three points which were previously validated were first interactively placed on the Mimics 3D model by the observer: the inferior tip of the scapula body, the center of the glenoid surface, and the medial pole of the scapula, as described by Kwon et al. (12) As described in detail below, these points were used to define the transverse scapular plane, based

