### **Primary Endpoints**

- Differences and/or similarities in glenoid erosion and version measurements between of 3D CT and 3D MR.

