### **Outcome Measure Evaluation Criteria**

- Degree of concordance/discordance between interpretation from 3D CT and 3D MR

CONFIDENTIAL

This material is the property of the NYU School of Medicine and Langone Medical Center.  
Do not disclose or use except as authorized in writing by the study sponsor (if applicable).

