#### CONFIDENTIAL

This material is the property of the NYU School of Medicine and Langone Medical Center.  
Do not disclose or use except as authorized in writing by the study sponsor (if applicable).

on which a new 2D CT image is generated. Each observer then manually selected the anterior and posterior aspect of the glenoid on this 3D-corrected image, and version was determined according to the Friedman et al. (17) The new CT image along the transverse scapular plane is generated according to the following procedure. The true coronal scapular plane passed through the 3 points. The scapular axis was defined as the line passing through the center of the glenoid and the medial pole of the scapula. The transverse scapular plane was perpendicular to the coronal scapular plane and passed through the scapular axis. A new CT image along the transverse scapular plane is generated from the original CT data set using the Vitrea workstation.

MRI is performed using 3T scanners with a dedicated 16-channel shoulder array coils. The MRI sequences include 3-mm slice thickness and 0.5-mm gap width with a field of view of 14 or 15 cm. There were 6 diagnostic sequences with axial, coronal, and sagittal proton density weighting as well as coronal T2 with frequency selective fat suppression and sagittal T1 images. The protocol also included an axial 3D dual echo-time T1-weighted FLASH sequence with Dixon-based water-fat separation with the following parameters: TR 10, TE 2.45/3.7, field of view of 200 mm, acquired voxel size 1.0×1.0×1.4 mm, reconstructed voxel size 1.0×1.0×1.0 mm, flip angle 9 deg, matrix 192×192, bandwidth of 400 Hz/pixel, number of partitions=120 and a slice thickness of 1mm.

MRI 3D Post-processing: The water-only source images from the Dixon sequence were post-processed using standard subtraction software on a syngo MMWP workstation (VB 3oE, Siemens). The lowest mean signal intensity (water min) from multiple ROIs placed on the soft tissues surrounding the osseous structures was used as a constant to calculate a subtraction image where the pixel values are subtracted from this constant (water\_min – SI (i) with negative values being set to zero). This resulted in images with increased signal in the osseous structures, surrounded by signal poor/void soft tissue structures. These subtracted Dixon images then underwent manual segmentation, generating 3D reconstructions of each shoulder (Tera Recon software (4.4.5.36.2068)).

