The 3D MRI glenoid version is measured by the two observers with the same method used for CT 3D glenoid version measurement following generating a new 2D axial MR images from the 3D MRI model using the three-point method as described above.

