### **Data Analysis**

Using SAS software, version 9.4 (SAS Institute Inc., Cary, NC, USA) Paired sample t-test to compare measurements by model and ANOVA to assess differences among modalities.

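### Readers are blinded only to each other: nothing masks or separates a patient's CT reading from the MR reading, so CT-MR agreement may be inflated, and the two blinding labels conflict.

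*Combined protocol and SAP*

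**What the plan says.** **Endpoint.** The primary endpoint (Section I, Primary Endpoints) is "Differences and/or similarities in glenoid erosion and version measurements" between 3D CT and 3D MR. The evaluation criterion in the next section is "Degree of concordance/discordance between interpretation from 3D CT and 3D MR". The stated aim is noninferiority of MR.

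**Readers and blinding.** Section III, Visit 2, assigns two musculoskeletal-trained radiologists. They measure version "on 2 occasions, at a minimum of 2 weeks apart, with the observers blinded to each other's results". This wording appears twice, once for 2D version and once for 3D CT version. For MR the text says: "The 3D MRI glenoid version is measured by the two observers with the same method used for CT 3D glenoid version measurement".

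**How the value is obtained.** Three landmarks are placed interactively on the 3D model. Then "Each observer then manually selected the anterior and posterior aspect of the glenoid on this 3D-corrected image". The MR model has a further manual step: "These subtracted Dixon images then underwent manual segmentation, generating 3D reconstructions of each shoulder". The plan does not say who segments or whether the CT is at hand.

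**Timing of scans.** "Subjects will have both 3D CT and 3D non-contrast MR scheduled on the same day".

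**Labels.** The Methodology row of the Study Summary calls the study single-blinded. The Study Design section calls it double blinded. Neither names the blinded party or what is concealed.

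**Analysis.** "Paired sample t-test to compare measurements by model and ANOVA to assess differences among modalities".

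**The concern.** Using the same two readers for both modalities is sound in a paired comparison and should stay. The difficulty is that the blinding described protects a different comparison from the one the study is about. Keeping observer A unaware of observer B's values makes the inter-reader comparison honest. It does nothing to keep observer A's MR value independent of observer A's CT value for the same patient.

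Version depends on where the operator places landmarks and glenoid edges, so knowledge of the CT answer, or of the CT images, can influence the MR answer. Followed to the letter, the plan lets an observer measure MR straight after the same patient's CT. If that draws MR toward CT, the differences shrink and concordance rises. A noninferiority conclusion against a margin, once one is set, becomes easier to reach. The error would favour the study's own hypothesis, and it could not be removed after the readings are done.

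**Working it through.** **Step 1. What each provision separates.** Every provision that might keep CT and MR readings apart was set against the comparison it protects.

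| Provision | Where | What it separates | CT from MR? |
|---|---|---|---|
| Observers blinded to each other | Visit 2, for 2D version and 3D CT version | Reader A from reader B | No |
| At least 2 weeks between occasions | Visit 2, same places | First from second read of one measurement | No |
| MR measured by the CT technique | Methods, 3D MRI version | At most carries the two rows above over to MR | No |
| Both scans on one day | Visit 2 | Nothing; it concerns acquisition | No |
| Coding of patient data | Data Storage and Confidentiality | Identity from stored records; readers not mentioned | No |
| Single-blinded / double blinded | Study Summary / Study Design | Undefined, and inconsistent with each other | Not stated |

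No provision masks the patient's CT values or images during MR reading, fixes a reading order, or sets a CT-to-MR interval. This step alone establishes the finding.

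**Step 2. Illustration of size.** The documents give no CT-MR mean difference, SD, margin or concordance cut-off, so there is no plan figure to reproduce. The only input from the documents is n = 50. The assumed inputs are:
- true mean CT-MR difference of 2 degrees
- limits of agreement 8 degrees either side of the mean, so SD = 8/1.96 = 4.08
- 5 degrees as a concordance cut-off
- one CT-MR difference per patient

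*Model A: anchoring.* The recorded MR value is (1 − w) × MR + w × CT. The recorded difference is then (1 − w) × (MR − CT), so mean and SD both scale by (1 − w).

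- Half-width of limits = 8(1 − w)
- Upper 95% confidence limit of the mean = (1 − w)(2 + 2.010 × 4.08/√50) = (1 − w) × 3.16
- Paired t = 2(1 − w) / [4.08(1 − w)/√50] = 3.46, because (1 − w) cancels
- Share within 5 degrees = normal probability that the difference lies between −5 and 5

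| w | Half-width (degrees) | Upper 95% limit (degrees) | Within 5 degrees | Paired t |
|---|---|---|---|---|
| 0 | 8.0 | 3.16 | 72.6% | 3.46 |
| 0.10 | 7.2 | 2.84 | 77.6% | 3.46 |
| 0.25 | 6.0 | 2.37 | 85.7% | 3.46 |
| 0.50 | 4.0 | 1.58 | 97.3% | 3.46 |

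Sensitivity to the assumed mean, for the same four values of w:
- mean 1 degree: 76.6%, 81.4%, 88.7%, 98.3% within 5 degrees; t = 1.73 throughout
- mean 3 degrees: 66.3%, 71.6%, 80.7%, 95.6% within 5 degrees; t = 5.20 throughout

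*Model B: correlated reading errors.* Suppose the whole SD is reading error, equal in the two modalities, with correlation ρ between a reader's CT and MR errors. The SD of the difference is multiplied by √(1 − ρ) and the mean is unchanged. At ρ = 0.5:
- SD = 4.08 × 0.707 = 2.89
- half-width = 8 × 0.707 = 5.66 degrees
- upper 95% limit = 2 + 2.010 × 2.89/√50 = 2.82 degrees
- share within 5 degrees = 84.3%
- paired t = 2/(2.89/√50) = 4.90

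Both mechanisms narrow the limits, lower the upper confidence limit and raise concordance. They differ only in the t statistic.

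**The case against.** The strongest objections, and what stands of each:

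- **The labels may have been meant to cover masking across modalities.** Possibly, but they contradict each other, neither is defined, and no procedure implements such masking.
- **The data could reveal anchoring.** Same-reader CT-MR differences could be compared with cross-reader ones (A's MR against B's CT), and CT-MR spread with each reader's own repeat-read spread. These checks are worth running. They are not decisive: stable reader habits mimic the first, and bias toward a correct CT value can escape both. The fair statement is that the data could not *reliably* show it.
- **The constant t statistic is built into the anchoring model.** This stands. Under correlated errors t rises, so the direction of the effect on the planned t-test depends on the mechanism. The direction for limits of agreement and concordance is the same in both models examined.
- **The illustrative inputs have no basis in the documents, and no noninferiority margin exists.** Both true. The figures should carry no weight in judging severity, and the harm to a margin-based conclusion is conditional on a margin being set. The concordance criterion is in the plan now.
- **Immediate MR reading is unlikely, because CT and MR are processed on different workstations and MR needs segmentation.** That makes it less likely but does not exclude it.
- **The argument covers version only.** Correct. The endpoint also names erosion, but the Methods describe no erosion measurement to assess.

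**Conclusion.** The concern holds. Blinding between observers is the only blinding procedure in the plan, the same two observers read both modalities by an operator-dependent method, and nothing masks or separates a patient's CT and MR readings. The single-blinded and double blinded labels conflict. These are facts of the text, and confidence in them is high.

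Inflated agreement is a risk that the design leaves open, not something the documents show to occur. Its size cannot be derived from them. Under the assumed inputs with a 2-degree mean, anchoring of 10% to 50% moves the share of patients within 5 degrees from 73% to between 78% and 97%; with no anchoring there is no bias. The change should be made because the risk bears directly on the primary endpoint, runs toward the study's hypothesis and is cheap to prevent.

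**What to change.** Keep the same two readers and the same number of readings. Amend the reading procedure in Section III (Visit 2 through the 3D MRI version paragraph) along these lines:

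> CT and MR image sets are de-identified and coded separately. Each observer reads CT and MR in separate sessions at least 2 weeks apart, in randomised case order with modality order balanced across patients, without access to the other modality's images or values, the other observer's values, or the reader's own earlier values. MR 3D models are prepared without reference to the CT.

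Readers will still recognise which modality is on the screen; what is masked is patient identity and the other modality's result. The 2-week interval matches the spacing already used for repeat reads, and another stated interval could be defended. Make the Study Summary and the Study Design section carry this same blinding statement, saying who is blinded to what.

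**Cost.** Protocol wording, separate coding of the image sets, a randomised reading list, and extra scheduling, since the existing 2-week spacing covers only repeat reads of one measurement. The reading period becomes somewhat longer and there is some image-preparation work. No patients, scans, readers or readings are added.

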## Study Summary

Title	Preoperative Magnetic Resonance as an Alternative to Computed Tomography Three-Dimensional Imaging for Characterizing Bone Loss in Shoulder Arthroplasty Candidates with Glenohumeral Osteoarthritis: A prospective, blinded, and controlled clinical trial.
Short Title	3D MR versus 3D CT in Glenohumeral Osteoarthritis
Protocol Number	S17-00500
Methodology	A prospective, unrandomized, single-blinded, self-controlled, and single-armed diagnostic radiological evaluation study.
Study Duration	12-Months
Study Center(s)	Single-Center
Purpose	To examine the non-inferiority of three-dimensional (3D) magnetic resonance (MR) versus the gold-standard, 3D computed tomography (CT) imaging, in the analysis of bone loss in shoulder arthroplasty (SA) candidates with glenohumeral osteoarthritis (OA). This study does not assess the safety and efficacy of MR imaging for musculoskeletal disorders.
Number of Subjects	50 subjects
Diagnosis and Main Inclusion Criteria	Patients with glenohumeral OA who are candidates for SA based on clinical examination with radiographic evidence of significant glenoid wear ; males and females age 18 and above.
Study Intervention and Planned Use	3D MR imaging of the shoulder for evaluation of glenoid bone loss.
Reference Intervention	3D CT imaging of the shoulder for evaluation of glenoid bone loss.
Statistical Methodology	Paired sample t-test to compare measurements by model and ANOVA to assess differences among modalities.

CONFIDENTIAL

This material is the property of the NYU School of Medicine and Langone Medical Center.  
Do not disclose or use except as authorized in writing by the study sponsor (if applicable).

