### **Objective**

1. The primary objective is to evaluate the noninferiority of 3D MR when compared to 3D CT for characterizing bone morphology in patients with glenohumeral osteoarthritis.

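### Repeat 3D CT version readings are planned but the analysis gives them no role, so a test of mean MR-CT difference cannot tell MR disagreement from CT's own reading error

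*Combined protocol and SAP*

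**What the plan says.** The Study Summary states the purpose as non-inferiority of MR "versus the gold-standard, 3D computed tomography (CT) imaging", and the Hypothesis is that the two give the same information.

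Under Visit 2, two radiologists read 3D CT version, blinded to each other: "The 3D glenoid version is measured by the same 2 observers on 2 occasions, at a minimum of 2 weeks apart". That is 2 × 2 = 4 readings per CT scan. Each reading depends on landmarks placed by the observer and glenoid edges picked by hand. After the MRI post-processing text, 3D MR version is "measured by the two observers with the same method used for CT 3D glenoid version measurement". The number of MR reading occasions is not stated separately.

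The Data Analysis section reads "Paired sample t-test to compare measurements by model", plus an ANOVA among modalities whose terms are not given. The Primary Endpoints and the Outcome Measure Evaluation Criteria likewise set MR against CT. Nothing says how the four readings are combined, plans observer reliability for either modality, or compares MR-CT disagreement with CT-CT disagreement. No margin and no reading-error SD is given.

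**The concern.** Whether MR can stand in for CT in an individual patient depends on how far an MR reading departs from a CT reading, relative to how far two CT readings of that shoulder already depart from each other. The repeat readings supply that yardstick, but no analysis uses it.

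A paired t-test asks whether the average MR-CT difference is zero. An MR that is right on average but scattered widely around CT satisfies that null hypothesis. If non-significance is then taken as support for the hypothesis of same information, a much noisier MR and an equally good MR receive the same verdict. Random CT reading error does not bias the mean difference, but it widens the SD of the differences and so makes a real MR bias harder to detect.

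**Working it through.** **Inputs from the protocol:** 50 patients (Number of Subjects); 2 observers × 2 occasions for CT (Visit 2); alpha .05 and power .80 (Sample Size Analysis). **Assumptions, because the protocol gives no figures:** single-reading error SDs of 0 to 3 degrees for CT and 1.5 to 4 for MR; a shoulder-by-observer SD s of 2 degrees shared fully by both modalities; normal errors; no average difference between observers.

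1. *The plan's own figure.* The protocol states "for alpha = .05 and power = .80, ten pairs are required, at minimum, for the study". With no effect size or SD, this can only be solved backwards. By the noncentral t distribution, ten pairs imply a mean difference of 0.996 SDs of the paired differences (two-sided) or 0.853 (one-sided). At 50 pairs these are 0.404 and 0.357. The figure concerns a mean difference and says nothing about scatter.

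2. *What the t-test sees.* For single readings, SD of difference = √(e_MR² + e_CT²), and 95% limits = ±1.96 × that SD. With e_CT = 2:
   - MR equal to CT: ±1.96 × √(4 + 4) = ±5.5 degrees, the same as CT against CT.
   - MR twice as noisy: ±1.96 × √(16 + 4) = ±8.8 degrees.

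   The true mean difference is zero in both, so the test rejects about 5% of the time in both. Simulation at n = 50 agrees.

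3. *Effect of CT error on power.* Take a true MR bias of 1 degree and e_MR = 1.5. With e_CT = 0 the SD of difference is 1.5; with e_CT = 3 it is √(2.25 + 9) = 3.35. Two-sided power falls from 0.996 to 0.54 at n = 50, and from 0.47 to about 0.14 at n = 10.

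4. *Attribution.* An observed MR-CT SD of 3 degrees implies an MR error SD of 3.0 if CT error is 0, but √(9 − 6.25) = 1.66 if CT error is 2.5. Only CT-CT readings distinguish these.

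5. *What the planned readings could show.* Between observers A and B, the expected mean squared differences are:
   - CT(A) against CT(B): 2s² + 2e_CT² = 8 + 8 = 16.
   - MR(A) against CT(B), and the reverse: 2s² + e_MR² + e_CT² + bias².
   - Excess of the second over the first: e_MR² − e_CT² + bias².

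   Simulated standard errors, n = 50, single readings averaged over occasion pairs, two occasions in both modalities, e_CT = 2:

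| MR case | Excess | SE |
|---|---|---|
| Equal to CT (e_MR = 2) | 0 | about 1.4 |
| Twice CT's error (e_MR = 4) | 16 − 4 = 12 | about 2.6 |
| 1.25 times CT's error (e_MR = 2.5) | 6.25 − 4 = 2.25 | about 1.7 |
| Equal error, 1-degree bias | 1 | about 1.5 |

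   With only one occasion per modality, the SEs in the first two rows rise to about 2.3 and 4.0.

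**The case against.** Several points against the concern are sound.

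- A reader might infer that the protocol treats CT as free of error. No passage says so. Calling CT the gold standard names the reference, and two blinded observers, two occasions and a technique meeting show that reading error was expected. A paired t-test also absorbs CT error into the SD of differences.
- A reader might also infer that noisy CT would make a good MR fail. Under the written analysis it would not: with MR equal to CT, rejection stays at about 5% whatever the reading SD. That failure needs an absolute agreement limit in degrees, and the protocol has none.
- It is tempting to say that the pairs will be formed so as to flatter MR, within observer or from averages. The protocol does not say how they are formed, and any figure rests on assumed variances.
- The danger of reading non-significance as sameness stems largely from using a difference test for non-inferiority without a margin. That is a separate and larger problem.
- The excess statistic is no cure-all. It mixes bias with noise, detects a 1-degree bias or a 25% increase in error poorly, and decides nothing without an acceptance bound.
- Reading MR by the same method plausibly carries over the two-occasion scheme, so that request is a clarification.

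What survives is that neither planned analysis, as written, addresses scatter around CT, and that the readings that would do so have no stated use.

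**Conclusion.** The concern holds as a gap in the planned analysis, not in the data. An unbiased MR with twice CT's reading error would pass unremarked about 95% of the time, a result that follows from the test itself and not from the assumed SDs. The loss of power from CT error and the precision of the excess statistic do depend on those SDs, and their true size is unknown. At 50 patients the planned readings could clearly reveal a doubling of error (12 / 2.6, about 4.6 standard errors) but not modest faults (2.25 / 1.7, about 1.3; 1 / 1.5, about 0.7).

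The scope is limited. The repeats are re-readings of one scan, so they measure reading error and not repeat-scan error. They are described for version only, so the erosion part of the primary endpoint has no such benchmark. The documents do not support a claim that CT is assumed exact, or that the plan is biased against a good MR. This is a worthwhile, inexpensive improvement.

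**What to change.** Add to Data Analysis a prespecified analysis of the planned 3D version readings that reports:

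1. the mean MR-CT difference with a 95% confidence interval;
2. CT-CT and MR-MR limits, within and between observers;
3. the between-observer MR-CT mean squared difference, MR(A) against CT(B) and MR(B) against CT(A), minus the CT(A)-CT(B) one. Use single readings averaged over occasion pairs, with a 95% confidence interval from bootstrapping patients, and interpret it against an acceptable excess that the sponsor sets and justifies beforehand.

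Report the mean difference beside the excess, because the excess alone detects small bias poorly. State in the MR measurement paragraph that MR is read on two occasions at least 2 weeks apart, as CT is, since the SEs of about 1.4 and 2.6 require it. State also that the benchmark covers version reading error only.

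The cost is a paragraph and some programming, with no additional patients or scans. If two MR occasions were not already intended, the second is extra reading time. The downside is that single-reading limits will look wider than limits from averaged readings.
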